Type of Study: Clinical trial (randomized, controlled and triple-blind).

MATERIAL AND METHODS.

Study universe: Mexican patients with prediabetes and overweight/obesity.

Study population: Mexican patients with prediabetes and overweight/obesity, from the State of Guanajuato.

Place of realization: Hospital Metabolism Laboratory of Division of Health Sciences of the University of Guanajuato, León, Gto.

Type of sampling: Non-probabilistic, of consecutive cases.

Sample size: The calculation of the sample size was based on the formula for comparing proportions. We hope that the low-dose combination of linagliptin + metformin will improve the outcome variables (insulin resistance, pancreatic beta cell function and cardiovascular function) by at least 75%, metformin use alone achieves this only by 30%(44.46), so the study is designed to detect a minimum difference of 45% between study groups with a type I (alpha) error of 0.05 and a sample power of 80% , and according to the following formula(70):

$$n = \frac{(Z\alpha/2 + Z\beta)^2 p^- (1-p^-)(r + 1)}{(d)^2 r}$$

Where,

$$(Z\alpha/2 + Z\beta)^2 = 7.9$$

p^1 = proportion of individuals in the best treatment who failed to achieve improvement = 0.25

p^2 = proportion of individuals in the worst treatment who failed to achieve improvement = 0.70

r = reason for individuals in treatment groups = 1

d = difference you're expected to find = 0.45

n = 14 + 20% of losses = 17 patients per group

SELECTION CRITERIA TO PARTICIPATE

- Women and men aged 18 to 65 overweight or obese (BMI 25 kg/m²)
- Patients with prediabetes, defined by:
 - 1) Glucose intolerance (ITG = glucose at 2h en la CTOG between 140-199mg/dL).

2) The coexistence of fasting impaired glucose (GAA = fasting glucose between 100 and 125mg/dl) and glucose intolerance (ITG = glucose at 2h in CTOG between 140-199mg/dL).

- Those who agree to participate in the study sign an informed consent letter.

NOT SELECTED TO PARTICIPATE

- Patients with DM2 previously diagnosed or detected during sampling and CTOG.
- People currently being treated or for the past 3 months with metformin, pioglitazone, or any other antidiabetic drug, including insulin.
- Serum creatinine >1.6mg/dl.
- Very high hipertriglyceridemia (>500mg/dl).
- Pregnant women.
- Uncontrolled arterial hypertension (systólic >180mmhg o diastolic >105mmHg).
- Excessive alcohol intake, acute or chronic.

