- Medications or medical conditions affecting glucose homeostasis (thiazides, beta blockers, systemic glucocorticoids, weight-reducing or anorexigenic drugs, Cushing syndrome, thyrotoxicosis)

ELIMINATION

- Intolerance to the medicine used.
- Absence to more than 20 % of follow-up appointments.
- That they do not finalize the study and monitoring protocol.

VARIABLES

INDEPENDENT VARIABLES

- 1) *Intervention*

DEPENDENT VARIABLES

- 1) *Glucose homeostasis.*
- 2) *Sensitivity to insulin.*
- 3) *Pancreatic beta cell function.*
- 4) *Cardiovascular function.*

OPERATION OF VARIABLES, MEASUREMENT SCALES AND MEASUREMENT UNITS.

DEPENDENT VARIABLE	CONCEPTUAL DEFINITION	OPERATIONAL DEFINITION	CLASIFICATION	MEASURE- MENT LEVEL	INDICATOR
INTERVENTION	It is the established therapeutic strategy to prevent the progression of Prediabetes to type 2 diabetes mellitus and its complications.	
A. Administration of 1 tablet of linagliptin 2.5 mg /metformin 850 mg every 24 hours + 1 tablet of metformin 850 mg every 24 hours.
 
B. Administration of 1 tablet of metformin 850 mg every 12 hours.
	Qualitative	Nominal	
A. Group with low dose treatment of Linagliptin/ Metformin.
 
B. Metformin treatment group.

DEPENDENT VARIABLE	CONCEPTUAL DEFINITION	OPERATIONAL DEFINITION	CLASIFICATION	MEASUREMENT LEVEL	INDICATOR
FUNCTION OF THE PANCREATIC BETA CELL	Pancreatic beta cell's ability to secrete enough Insulin to keep blood glucose levels at normal levels.	Value obtained by the CTOG, when applying the formula $(\Delta I_{0-30})/(\Delta G_{0-30})$, (ΔI_{0-30}) = difference in insulin value measured at 0 and 30 minutes. (ΔG_{0-30}) = difference in glucose value measured at 0 and 30 minutes.	Quantitative	Reason	Pmol/mmol,
HOMEOSTASIS OF GLUCOSE	Ability of therapeutic interventions to reverse glucose intolerance.	It shall be considered as YES when the fasting glucose level at 6 months after the intervention begins, either at 2 h during CTOG is <140mg/dL, and NO when glucose levels at 2h during CTOG are 140mg/dL.	Qualitative	Dichotomous Nominal	Yes No

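### The 20% loss allowance multiplies 14 by 1.20 instead of dividing by 0.80, so 17 per group covers 17.6% losses among those enrolled: a small slip beside the larger error in the 14 itself

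*Combined protocol and SAP*

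**What the plan says.** Under Material and Methods, Sample size, the plan compares two proportions with "type I (alpha) error of 0.05 and a sample power of 80" per cent. The inputs are:

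- "proportion of individuals in the best treatment who failed to achieve improvement = 0.25";
- "proportion of individuals in the worst treatment who failed to achieve improvement = 0.70";
- "d = difference you're expected to find = 0.45";
- "r = reason for individuals in treatment groups = 1", that is, equal allocation;
- a squared sum of normal quantiles, written with alpha/2, set at 7.9.

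The paragraph closes with "n = 14 + 20% of losses = 17 patients per group". It does not say what the 20% is a percentage of.

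The Elimination section removes patients for intolerance, for missing more than 20% of follow-up appointments, and for non-completion ("That they do not finalize the study and monitoring protocol"). The Statistic Analysis section plans both an intention-to-treat and a per-protocol analysis and gives no method for missing outcomes.

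**The concern.** A loss allowance should make the number remaining equal the number that the power calculation needs. If a fraction L of enrolled patients is lost, n evaluable requires n/(1 - L) enrolled. Multiplying by (1 + L) always gives less than this. Here the plan multiplied.

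All three elimination criteria can apply only to people already in the trial, so enrolled patients are the natural base for the percentage. On that base, the stated protection against 20% losses is not quite delivered. The slip also does not depend on whether 14 is right. If the evaluable number is corrected and the same loss step is kept, the new enrolment figure will again be too low.

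**Working it through.** **The plan's loss step, reproduced.** 14 x 1.20 = 16.8, rounded up to 17. This matches the stated figure.

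**The loss step on enrolled patients.** 14/(1 - 0.20) = 17.5, so 18 per group.

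| Enrolled per group | Expected evaluable at 20% loss | Most losses that still leave 14 |
|---|---|---|
| 17 | 17 x 0.80 = 13.6 | 3 (3/17 = 17.6%) |
| 18 | 18 x 0.80 = 14.4 | 4 (4/18 = 22.2%) |

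The shortfall at 17 is 14 - 13.6 = 0.4 patient per arm. A fourth loss takes an arm to 13, but 4/17 is 23.5%, not 20%.

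**Cost in power by the printed formula.** The formula is n = K x pbar x (1 - pbar) x (r + 1)/(d^2 x r), where K is the squared sum of quantiles. Inputs from the sample-size paragraph: pbar = (0.25 + 0.70)/2 = 0.475, d = 0.45, r = 1. Then pbar x (1 - pbar) x 2 = 0.475 x 0.525 x 2 = 0.49875, and d^2 = 0.2025. Solving for power with a two-sided alpha of 0.05:

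power = Phi( sqrt(n x 0.2025/0.49875) - 1.96 )

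| Evaluable per group | Square root | Minus 1.96 | Power |
|---|---|---|---|
| 14 | 2.384 | 0.424 | 66.4% |
| 13.6 | 2.350 | 0.390 | 65.2% |
| 13 | 2.297 | 0.337 | 63.2% |

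A loss of 20% therefore costs 66.4 - 65.2 = 1.2 points relative to 14. A normal approximation with a different variance treatment gives 68.3% at 14 and 66.9% at 13.6, a difference of 1.4 points. The size of the effect does not depend on the variant.

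**Chance variation.** Assume that each patient independently has a 20% chance of loss. The number lost in an arm of 17 is then Binomial(17, 0.20), with median and mode 3, which leaves exactly 14. An arm of 17 keeps at least 14 with probability 0.549, and both arms do so with probability 0.549^2 = 0.30. With 18 these figures are 0.716 and 0.51.

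**The number being inflated.** With the plan's own inputs, n = 7.9 x 0.49875/0.2025 = 19.46, so 20 per group. The stated 14 does not follow from the printed formula. The loss step applied to 20:

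- multiplied: 20 x 1.20 = 24, and 24 x 0.80 = 19.2, which is below 20;
- divided: 20/0.80 = 25, and 25 x 0.80 = 20.

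**The case against.** The strongest reply is that the plan never says 20% of those enrolled. Read literally, it adds 20% of 14, which is 2.8 or about 3 patients, and 17 - 3 = 14. On that reading nothing is missed. This stands as a possible reading, so the conclusion has to be conditional. But it explains how 17 was reached more than what protection it gives: a reader will take 20% as a dropout rate among participants, and the elimination criteria point the same way.

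A second reply is that the intention-to-treat analysis keeps everyone. That carries limited weight. The plan eliminates non-completers, gives no method for missing outcomes, and needs a final glucose tolerance test and echocardiogram at 6 months. The per-protocol set shrinks in any case.

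Three stronger readings are tempting, and the documents do not support them:

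- *That 20% losses leave 13 per arm.* They leave 13.6 in expectation. Thirteen needs four losses, or 23.5%, so the 63.2% power at 13 is not the cost of a 20% loss.
- *That the 0.55 and 0.30 probabilities measure the error.* They mostly reflect chance. With 18 per arm, at least one arm still falls below 14 about half the time (1 - 0.51 = 0.49).
- *That this slip is why the trial lacks 80% power.* It is not. Full retention of 14 gives 66.4% by the printed formula, and moving to 18 enrolled (14.4 expected) would not restore 80%. That deficit comes from the 14.

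**Conclusion.** The concern holds in a limited form. The 17 comes from multiplying by 1.20. If the 20% is a share of enrolled patients, the step should give 18, and 17 per group supports losses of 17.6% and not 20%. The shortfall is 0.4 patient per arm and about 1 point of power.

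This rests on two assumptions: that enrolled patients are the base for the percentage, which the plan implies but does not state, and that lost patients contribute no 6-month outcome.

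The point is minor and belongs beside the base-number error. The plan's formula and inputs give 20 evaluable per group, and correcting both steps gives 25 enrolled per group (50 in all) against the stated 17 (34 in all). Correcting the loss step alone changes little, but correcting the base alone would carry the slip forward and give 24.

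**What to change.** Restate the closing line of the sample-size paragraph to say that 17 per group allows 3 losses (17.6%) before falling below 14, and that losing 20% of those enrolled leaves 13.6 expected evaluable. Quote the power at that number, 65.2% by the printed formula, in place of 80%. State that the 20% refers to enrolled patients. This costs one corrected line and a less favourable stated power, with no extra patients.

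Make the change together with the correction of the base number, because restating the tolerance around 14 would otherwise leave an unsupported planning figure in place. In any revision use n/(1 - 0.20): from 20 evaluable this gives 25 per group. Relative to adding 20%, the correct loss step costs one patient per group (25 against 24). The rest of the increase from 17 comes from the base number. If enrolment cannot be changed, the restated tolerance and power should stand as the plan's acknowledged limits.

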Patients with CTOG glucose intolerance are those who will be invited to participate in the trial and those who accept will continue with a more thorough metabolic evaluation. For this purpose, patients will have completed a medical history and the following studies:

1) Fasting basal blood samples for measurement of:

- Blood count
- Lipid profile
- Insulin for homa-IR determination, HOMA-B, insulin sensitivity, insulin secretion and pancreatic beta cell function.

2) Determination of body composition (% visceral fat, % total body water, bone mineral density, etc.) using DEXA analysis. Here the patient scrutiny ends and if at this time the patient agrees to participate in the phase of intervention, the following will be carried out, after explanation and signature of informed consent letter.

- 1) Cardiovascular function assessment: This will be done through standard echocardiography area of the High Specialty Regional Hospital.
- 2) Evaluation of renal function: Through 24-hour urine collection, which will measure creatinine clearance and 24-hour albuminuria.
- 3) Randomization: It will be done by using a table of random numbers generated by a computer program. Patients will be randomized to receive, for 6 months, one of the following 2 interventions: 1) Dosis of *linagliptin 2.5 mg* every 24 h + *metformin 1700 mg* every 24 h y 2) 1 tablet every 12 h of Metformin 850mg.

THIRD PHASE: *Intervention and follow-up*

All patients will receive nutritional guidance and physical activation during the study. Once patients have all baseline measurements and have met the selection criteria, they will be randomized to one of the two interventions. All patients will have monthly follow-up and global clinical evaluation and treatment attachment, and anthropometry.

FOURTH PHASE: *Ending of the study (final measurements)*.

At 6 months of treatment, patients will be quoted again in fasting, on two different occasions,

- 1) FIRST APPOINTMENT: For measurement of glucose and fasting insulin, determination of body composition by imdoanciometry and performance of CTOG.
- 2) SECOND APPOINTMENT: Evaluation of cardiovascular function by echocardiography, and renal function by depurating creatiline and albumin in urine of 24h.

STATISTIC ANALYSIS

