The data will be presented with descriptive statistics, mean and standard or median deviation and interquartile travel, as well as percentages and incidence. For comparisons of numeric variables between study groups, we will use Student t if the distribution of the data follows a normality pattern, otherwise the Mann-whitney U test will be used; to compare qualitative variables we'll use square Chi. Analysis by intent to be treated and analyzed by protocol shall be performed and considered as significant when the p-value is <0.05. For the analysis and presentation of the data we will use the sPSS Version 15 and GraphPad Prism program 5.

ETHICAL ASPECTS

Ethical standards, Regulations of the General Health Law on Health Research and the Helsinki Declaration of the World Medical Association of the 64th General Assembly, StrongHold, Brazil in 2013 and current international codes and standards of good clinical research practices. Special attention will be given to taking care of the privacy and

autonomy of the patient. Once the patient has been informed about the study and agrees to participate in it, and since it involves a greater risk to a minimum, the signature of informed consent letter will be requested.

BIBLIOGRAPHIC REFERENCES:

4. Villalpando S, de la Cruz V, Rojas R, Shamah-Levy T, Avila MA, Gaona B, et al. Prevalence and distribution of type 2 diabetes mellitus in Mexican adult population: a probabilistic survey. *Salud Publica Mex* [Internet]. 2010 [cited 2018 Apr 7];52 Suppl 1:S19-26. Available from: <http://www.ncbi.nlm.nih.gov/pubmed/20585724>

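### Randomised patients can be eliminated for intolerance, absence or non-completion, but the plan does not say from what, so the promised intention-to-treat analysis could shrink towards a completers' analysis

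*Combined protocol and SAP*

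**What the plan says.** The protocol's Elimination list stands apart from the exclusion criteria and has three entries: "Intolerance to the medicine used", "Absence to more than 20 % of follow-up appointments" and "That they do not finalize the study and monitoring protocol". It adds no explanation.

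The Statistic Analysis section says "Analysis by intent to be treated and analyzed by protocol shall be performed". It describes neither set, does not say which is the main one, does not mention the Elimination list, and has no rule for missing values. On methods it says "For comparisons of numeric variables between study groups, we will use Student t if the distribution of the data follows a normality pattern", with Mann-Whitney otherwise and chi-square for qualitative variables.

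On timing, the Randomization item says "Patients will be randomized to receive, for 6 months, one of the following 2 interventions". During treatment, "All patients will have monthly follow-up and global clinical evaluation and treatment attachment, and anthropometry". The outcome tests come at the end: "At 6 months of treatment, patients will be quoted again in fasting, on two different occasions". The first of these appointments covers the oral glucose tolerance test (CTOG), fasting samples and body composition. The second covers echocardiography and the 24-hour urine.

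The Sample size paragraph requires 14 per group and adds 20% for losses, giving 17.

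**The concern.** Intolerance, attendance and completion are all observed after randomisation, and each can depend on the assigned drug or on the response to it. A comparison restricted to those who tolerated the drug, attended and finished is no longer the comparison that randomisation protects.

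The plan promises an intention-to-treat analysis, but that promise needs 6-month values from patients who stopped or missed visits, or a rule for when those values are absent. The plan secures neither. If elimination is taken to include not being measured at 6 months, the two promised analyses would use almost the same patients. If they do differ, nothing fixes in advance which one is reported as the result. Unlike an analysis rule, a 6-month measurement that was never taken cannot be supplied later.

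**Working it through.** **1. Do the criteria act after randomisation?** Study drug and monthly follow-up start after randomisation, and no run-in is described. All three criteria therefore apply to randomised patients. Monthly follow-up for 6 months implies about six visits: one absence is 1/6 = 17%, below the limit, and two are 2/6 = 33%, above it.

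**2. Is there an earlier outcome value to fall back on?** The monthly visits list clinical evaluation, adherence and anthropometry. The CTOG and echocardiogram appear only at baseline and at 6 months. The planned t, Mann-Whitney and chi-square comparisons at the end of treatment therefore need the 6-month value.

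**3. The plan's loss allowance.** 14 × 1.2 = 16.8, rounded to 17, which reproduces the stated step. It corresponds to 17 − 14 = 3 lost per arm, used below. (The 14 itself does not follow from the printed formula: 7.9 × 0.475 × 0.525 × 2 / 0.45² = 19.5, that is 20 per group. That is a separate matter. Here 14 and 17 are taken as given.)

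**4. Illustration for the yes/no outcome.** Glucose homeostasis is the only dichotomous dependent variable, and the plan gives no expected proportions for it. The counts below are assumptions: 10/14 v 4/14 improved among completers (combination v metformin), with 3 lost per arm. Pearson chi-square = N(ad − bc)² / (product of the four margins), without continuity correction:

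| Handling of the 3 lost per arm | Counts | Chi-square | p |
|---|---|---|---|
| Left out | 10/14 v 4/14 | 28 × 84² / 14⁴ = 5.14 | 0.023 |
| Failures in both arms | 10/17 v 4/17 | 34 × 102² / (17² × 14 × 20) = 4.37 | 0.037 |
| Adverse extreme: combination fail, metformin improve | 10/17 v 7/17 | 34 × 51² / 17⁴ = 1.06 | 0.30 |

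The differences in proportions are 0.43, 0.35 and 0.18. Fisher's exact test on the same tables gives 0.057, 0.080 and 0.49. The table therefore shows how far handling can move the result; it is not a forecast of significance.

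**5. Illustration for the quantitative outcomes.** Suppose 3 of 17 are lost in one arm only, and they differ on average by 0.5 to 1.0 SD from the 14 who stay. The gap is an assumption; the documents give none. The shift in the group difference is (3/17) × 0.5 = 0.09 SD to (3/17) × 1.0 = 0.18 SD. The standard error of the difference is √(1/14 + 1/17) = 0.36 SD. The shift is thus 0.24 to 0.49 of one standard error. Equal loss with an equal gap in both arms cancels.

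**The case against.** The best defence is that the Elimination list is simply the per-protocol filter. That reading makes the sentence promising both analyses coherent. The text also speaks of all patients being followed monthly and of patients being recalled at 6 months, with no exception for those eliminated. Adding 20% for losses is ordinary inflation and does not show that eliminated patients go unmeasured. This reading is possible, but no section states it, and the monthly visits do not measure the CTOG or echocardiographic outcomes.

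Arm-related elimination is also made less likely by the design. Both arms take metformin 1700 mg/day, so metformin intolerance is shared. The background on side effects reports no excess for DPP-IV inhibitors over control groups, and the trial is described as triple-blind. These points stand as mitigation. They do not exclude the problem: the side-effect statement is not specific to prediabetes, the plan does not say who is blinded, blinding does not cure informative loss, and attendance or completion may still follow response.

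A reader might infer that the intention-to-treat analysis will in fact drop eliminated patients. The documents do not say so. A reader might also apply the sample-size rates of 75% and 30% to claim that the planned result is fragile. Those rates are stated for insulin resistance, beta-cell function and cardiovascular function, which the variables table classes as quantitative and which would not be compared by chi-square. They give no basis for such a claim.

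**Conclusion.** The gap is real: the plan does not say what patients are eliminated from, defines and ranks neither analysis set, and has no rule for missing 6-month values. If eliminated patients are not measured at 6 months, intention-to-treat would nearly coincide with completers and be open to selection bias. That condition is an inference, and the size and direction of any bias are unknown.

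In the hypothetical yes/no example, counting losses as failures in both arms leaves the result on the same side of 0.05; only the extreme adverse assignment moves it far. For the quantitative outcomes the assumed shift is at most about half a standard error and requires unequal loss or unequal gaps. The documents therefore do not support saying that the trial's conclusion would be reversed. The point is a cheap improvement that secures data which cannot be obtained later.

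**What to change.** 1. State that, for analysis purposes, the Elimination list serves only to define the per-protocol set. Decisions on treatment are left as they are.
2. Invite every randomised patient who has not withdrawn consent to the two planned 6-month appointments, whether or not treatment stopped or visits were missed.
3. Name intention-to-treat by randomised arm as the main analysis and per-protocol as the sensitivity analysis.
4. Report losses and reasons by arm, and state one missing-data rule with one sensitivity analysis. Examples are counting missing as failure in both arms for glucose homeostasis, and a shift of 0.5 to 1.0 SD for the quantitative outcomes.

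The cost is protocol wording, a little analysis, and up to about 3 patients × 2 arms × 2 appointments = 12 extra attendances if the planned losses occur and all return. Those attendances carry the CTOG with its five samples, echocardiography and the 24-hour urine. Patients measured off treatment may dilute the difference; comparison with the per-protocol analysis gives an indication of how much. Some will not return, so step 4 is needed even if step 2 is adopted.

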SENSITIVITY TO INSULIN	Insulin's ability to promote glucose uptake by muscle tissue, and suppress glucose production by the liver and avoid the lipolysis in adipose tissue.	It will be evaluated using Matsuda's index with glucose and insulin values during CTOG using the following formula: Insulin sensitivity = $\frac{10000}{\sqrt{(G_0 \times I_0) \times (\bar{G}_{0-120} \times \bar{I}_{0-120})}}$	Quantitative	Reason	Natural numbers

CARDIO-VASCULAR FUNCTION	Function of the system made up of heart and blood vessels for transport activities.	Measurement of ejection fraction, diastolic and systolic preloads and ejection fraction.	Quantitative	Continues	Percentage %
--------------------------	---	--	--------------	-----------	--------------

METHODS.

Identification of patients at risk

During this initial phase, overweight or obese patients will be identified with and at least 2 risk factors for DM 2, who will be invited to the screening of the study and as a first step will answer a survey of nutrition and physical activity.

Recruitment of patients

Metabolic evaluation and classification of patients: Once obtaining weight and size, we identify overweight or obese patients and risk factors for DM2, they will be invited to continue the counting phase; The next step will be to cite patients for fast glucose measurement, and only patients who have a glucose level of 100mg/dL will have CTOG performed to determine the presence of prediabetes.

Glucose tolerance curve: The tolerance curve consists of citing the patient with an 8-12 hrs fast, the vein is channeled to the ulnar with 0.9% 250cc saline solution, basal blood samples are taken and 75g of glucose is given to drink and subsequently take blood samples every 30 minutes for the next two hours (0, 30, 60, 90 and 120min), for glucose determination at that time and for subsequent measurement of insulin, glucagon and GLP-1. As mentioned in the selection criteria, patients who are diagnosed with DM2 during screening (CTOG) will not be included in the study.

According to glucose values within 2 hours of oral loading, patients will be classified as:

- 1) Glucose-tolerant norms when glucose at 2hrs during CTOG is <140mg/dl,
- 2) Patients with glucose intolerance when glucose at 2hrs of CTOG is between 140 and 199mg/dL,

3) Recently diagnosed DM2 patients when glucose is 2 hrs. CTOG is 200mg/dL.

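### Glucose homeostasis is planned only as a Yes/No cut at 140 mg/dL compared by chi-square; adding a baseline-adjusted comparison of the 2-h glucose already measured would gain precision for this one outcome

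*Combined protocol and SAP*

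**What the plan says.** Under Variables, glucose homeostasis is the first of four dependent variables. In the table of operational definitions its concept is reversal of glucose intolerance, it is classed as qualitative and dichotomous, and it is scored from the 6-month tolerance test. YES is below 140 mg/dL, "and NO when glucose levels at 2h during CTOG are 140mg/dL". The comparison sign before the last figure seems to have been lost in extraction; I read it as 140 or above and do not count it as an error. The other three dependent variables are quantitative.

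Under Statistic Analysis, numeric variables are compared by Student t or Mann-Whitney, and chi-square is used "to compare qualitative variables". No covariate, change score or model with baseline appears.

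Under Glucose tolerance curve, staff "subsequently take blood samples every 30 minutes for the next two hours (0, 30, 60, 90 and 120min), for glucose determination". The test decides entry, with a 2-h glucose of 140-199 mg/dL required, and is repeated at the first appointment of the fourth phase. One specific objective concerns glucose metabolism by the tolerance curve at baseline and at the end of treatment. No variable or test is attached to that objective.

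**The concern.** All patients start at or above the cut, at very different distances from it. In whole mg/dL, a patient who enters at 142 becomes a YES with a fall of 3, while one who enters at 197 needs a fall of 58. The Yes/No score treats 139 and 90 as the same result, and 141 and 195 as the same result. Chi-square then uses neither the size of the change nor the starting value.

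With 14 to 17 patients per arm, this is a costly way to compare a measurement that is already available as a number at both times. At stake is the chance of detecting a real difference in 2-h glucose, and how far the result depends on which arm happens to start nearer to 140.

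**Working it through.** **The plan's own figure.** The sample size is for proportions, with "type I (alpha) error of 0.05 and a sample power of 80"% and failure rates of 0.25 and 0.70. The printed formula gives 7.9 × 0.475 × 0.525 × 2 / 0.45² = 19.5 per group, not the stated 14; the step 14 × 1.2 = 16.8, rounded to 17, does follow. That mismatch is a separate matter. Here 14 and 17 serve only as the planned group sizes.

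**Large-sample efficiency of a cut.** For a normal variable split so that a share p respond, the efficiency relative to the continuous value is φ(z_p)² / [p(1 − p)].

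| Share responding | Efficiency | Loss |
|---|---|---|
| 50% | 0.637 | 36% |
| 40% or 60% | 0.622 | 38% |
| 30% or 70% | 0.576 | 42% |
| 25% or 75% | 0.539 | 46% |
| 20% or 80% | 0.490 | 51% |

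**A specific contrast.** The documents give no expected reversal rate. For illustration I borrow the 30% and 75% improvement rates that the sample-size section uses for other outcomes.

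- If these are the shares of a normal 2-h glucose below 140 with equal SD, the standardised difference is z(0.75) − z(0.30) = 0.674 + 0.524 = 1.199.
- Continuous comparison: 2 × (1.96 + 0.84)² / 1.199² = 10.9 per group.
- Comparison of proportions (pooled variance under the null, unpooled under the alternative): 18.1 per group.
- Ratio 10.9 / 18.1 = 0.603, a loss of about 40%.
- Exact small-sample power: the t test reaches 80% at 12 per group, Pearson chi-square at 17 to 18. The loss is then 1 − 12/17 = 29% to 1 − 12/18 = 33%.

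A fair summary is roughly 30-45%, and more if reversal is rare or nearly universal.

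**Simulation with the baseline value.** All inputs are assumptions: baseline uniform on 140-199 mg/dL, control 6-month mean 150, slope on baseline 0.5, residual SD 25, true benefit 25 mg/dL. Results are from 6,000 trials per cell, two-sided 5%.

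| Per arm | Chi-square | t test | ANCOVA |
|---|---|---|---|
| 17 | 61% | 77% | 79% |
| 14 | 46% | 67% | 70% |

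- For residual SD 20-30 and benefit 20-30 mg/dL, ANCOVA gains about 11-21 points over chi-square at 17 per arm and about 15-29 at 14.
- For a benefit of 10-15 mg/dL, the gain at 17 per arm is about 3-18 points, and no analysis has more than about 55% power.
- The ends of these ranges move by a point or two between runs.
- With no true benefit, all three methods reject in about 4-5% of trials.

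**How much reversal depends on the starting value.** In the same model the control mean is 150 + 0.5 × (142 − 169.5) = 136.25 for a patient starting at 142, so P(YES) = Φ(3.75/25) = 56%. For one starting at 197 the mean is 163.75 and P(YES) = Φ(−23.75/25) = 17%.

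**The case against.** Reversal of intolerance is the concept that the plan sets out to measure, and 140 mg/dL is the plan's own diagnostic boundary, not a cut chosen from data. A reader might infer that the Yes/No comparison should be dropped or reduced to description. The documents do not support that, because it would change the stated question. This stands, so the reversal comparison should stay.

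The reach is limited. The problem statement, hypothesis, general objective and sample size name beta cell function, insulin resistance and cardiovascular function, all of which are analysed as quantitative. A reader might infer that the trial's main comparison is dichotomised; it is not.

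The tolerance-curve objective, together with the general rule for numeric variables, leaves room for a t test or Mann-Whitney comparison of 2-h glucose. So the plan cannot be said to throw the numbers away. It leaves that comparison unspecified, which is a weaker charge but still a gap.

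The contrast between starting at 142 and at 197 might suggest bias. Randomisation makes such differences a matter of chance, and chi-square kept its type I error near 5%. Adjustment itself adds little in the central scenario: about 2 of the 18 points gained at 17 per arm, and about 3 of the 24 at 14.

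Finally, the documents give no SD, reversal rate, baseline correlation or expected benefit for 2-h glucose. The size of the gain is therefore conditional. Its direction was the same in every scenario tried with a true benefit.

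**Conclusion.** The point holds as an inexpensive gain in precision for one listed outcome. It does not threaten the validity of the trial. Glucose homeostasis has only a Yes/No definition, a chi-square comparison and no use of baseline, while the numeric value exists at both times with no prespecified analysis.

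The 30-45% loss assumes an approximately normal 2-h glucose with equal SD in the arms. Its upper part is a large-sample figure, and the exact small-sample check sits near 30%. A flat figure of 40% would claim more than the documents allow. The power gains rest on the stated simulation inputs and shrink when the benefit over metformin is small.

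**What to change.** In the table of operational definitions, add 6-month 2-h glucose in mg/dL as a quantitative variable under glucose homeostasis, and link it to the tolerance-curve objective. In Statistic Analysis, specify a between-arm ANCOVA of that value with baseline 2-h glucose as covariate, reported as an adjusted difference with 95% confidence interval. Describe it as the more sensitive analysis of this outcome. Keep the Yes/No reversal comparison beside it, and state in advance which of the two is the main analysis, so that the choice cannot follow the results.

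The change needs no new visit, sample or patient. The downside is one more analysis to report, and one of the two must be named as main.
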